### ***Secondary effectiveness, maintenance and reach outcomes***

The analytical model for the primary aim will be modified to assess these aims by making the secondary student outcomes the dependent variables. For nonlinear outcomes, such as discrete health literacy classification, appropriate link functions will be used in the multilevel model. Also, the time indicator in the model will be changed to examine effectiveness at 3-month, 7-month, and 19-month. For caregivers' outcome analysis, a simplified version of the above multilevel mixed effect selection models will be applied, recognizing the class nesting will not be of concern for this level. Furthermore, an additional indicator that signals the uptake of the SMS will be added to the model to examine the adoption of SMS influence on caregivers' behavior and home environment changes. To further explore student-caregiver dynamics, mixed effect structural equation models will examine the causal relationship among caregiver and student SSB outcome changes. Finally, differences in student effectiveness data will be explored by comparing student level changes within schools when Kids SIPsmartER is co-delivered by researchers-teachers versus when delivered by teachers only.

The program reach at student and caregiver levels will be analyzed following recommendations of Glasgow and colleagues. Participation rate at each school will be determined by dividing the total number of 7th grade students and caregivers enrolled by the total number eligible to enroll. Representativeness will be assessed by comparing demographics of students and caregivers eligible and enrolled to the demographic data provided by schools. Uptake/utilization of SMS among caregivers will also be analyzed.

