- Primary effectiveness aim: assess changes in SSB behaviors at 7-months (immediately post program) among students receiving Kids SIPsmartER, as compared to control schools. Secondary aims:
- Secondary effectiveness & maintenance outcomes: determine changes in secondary student outcomes (e.g. quality of life,

BMI z-score, theory-related variables, health and media literacy); changes in caregiver SSB behaviors and home environment; and maintenance of outcomes at 19-months post-baseline.

- Reach: assess the reach and representativeness of Kids SIPsmartER, among students and parents/guardians.
- Implementation, adoption, and school-level maintenance: using a mixed-methods approach with interviews, surveys, observation, and process evaluation strategies, assess the degree to which teachers implement Kids SIPsmartER as intended and the potential for institutionalization within the schools.

If found to be effective among students, and if implementation at the school level shows strong potential, our mid-term goal is scale up Kids SIPsmartER to reach additional middle schools. The long-term goal of this line of health promotion and prevention research is to sustain multi-level strategies to reduce SSB-related health inequities and chronic conditions (e.g. obesity, cancer, diabetes, dental decay) in rural Appalachia.

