The measurement packets are the same regardless of intervention or control schools. With the exception of intervention school participants answering questions about their experience with the Kids SIPsmartER program.

See Attachment #2. Data consists of:

Beverage Behaviors, including SSBs (BEV-Q)  
 SSB Theory of Planned Behavior  
 SSB Media Literacy  
 Health Literacy & Numeracy, Newest Vital Sign  
 Public Health Literacy  
 Quality of Life  
 SSB Home Environment  
 SSB Parenting Practices/Rules  
 Satisfaction Questions

At the 7-month assessment, students will receive a nominal prize, valued at \$5.50 (such as Kids SIPsmartER t-shirt, see budget).

MODIFICATION 3/16 DUE to coronavirus and school closure: We are requesting a modification to allow for flexibility in working with each of our enrolled schools to distribute and collect student surveys for our primary outcome data point. There will be no change to the content of the survey, but the student survey may be distributed and returned via mail or via an on-line Qualtrics links (using UV Qualtrics Research Suite) sent to the students. Knowing that each school and student's within schools will have different capabilities for an on-line survey, we will work closely with each school to follow their recommendations.

[AMENDMENT July 2021] Student Assessment Packet (SupS2)

Describe this Data Source. What does/will the data consist of? If a data set will be used, include the data fields to be used.

Students (SupS2). For students during these years, we will administer the survey instruments during class time at 3 times [baseline, 3-months, and 7-months]. At 3-months, only the self-reported SSB behaviors will be assessed. To ensure efficiency and improve the quality of data, the survey will be delivered and student response recorded using an Audience Response System. Based on our experience, we anticipate that each survey assessment data point will take half of one class period, or ~20-25 minutes.

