See Attachment #37. Survey questions include Beverage Behaviors, including SSBs (BEV-Q), SSB Theory of Planned Behavior, SSB Media Literacy, Public Health Literacy, Quality of Life, SSB Home Environment, and Satisfaction Questions [7-month only]. Compared to the original student survey (Attachment #2), 36 items were removed. Items were removed to streamline the survey to focus on SSB related questions and remove identifiers. Removed items relate to specifics of household rules about sugary drinks (9 items), household availability of food items (3 items), perceptions of weight (2 items), physical activity behaviors (3 items), dietary pattern (11 items), oral health behaviors (3 items), sleep behaviors (3 items), school performance (1 item), and month and day of birth (1 item)

[August 2024 Modification] See Attachment #40. This shortened version of the survey replaces Attachment #37. Survey questions include Beverage Behaviors, including SSBs (BEV-Q), SSB Theory of Planned Behavior, SSB Home Environment, and Satisfaction Questions [included at 7-month only]. Compared to the previously used survey (Attachment #37), 36 items were removed. Items were removed to streamline the survey to focus on key SSB-related questions and reduce burden on teachers. Removed items relate to specifics of household rules about sugary drinks (15 items), media literacy (6 items), health literacy (6 items), public health literacy (4 items), and quality of life (5 items).

To be flexible to school preference for survey distribution and in case of future virtual learning due to school closures to in-person learning (i.e., COVID-19 related closures), there will be two modes of delivery for student surveys: pen and paper and on-line via a Qualtrics link (using UVA Qualtrics Research Suite). Knowing that each school and student's within schools will have different capabilities for an on-line survey, we will work closely with each school to follow their recommendations.

[MODIFICATION August 10 2021]" We collect MM/DD/YYYY on surveys for consented/assented students and enrolled parents/caregivers but only collect YYYY for the students who have waiver of consent. Birthdate detail is needed to calculate student BMI.

**Will a recording device (e.g. audio, video, photographic) be used to collect data/materials from participants?** No

**Are the participant's identifying information included as part of the data at any time?** Yes, and participant identifiers will NOT retained

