### Power calculation and sample size

Given the lack of interventions and designs similar to Kids SIPsmartER, data from the Kids SIPsmartER feasibility study were used to estimate the effect size and intraclass correlation (ICC) of students' SSB intake. Considering the school size eligibility criteria and anticipated variation in the number of students per school (range 80-200 students, average 133 students), a lower and upper range of power is estimated. Due to the cluster-randomized block design (i.e., randomization at school level), no attrition at the school level is anticipated. The sample size calculations are conservatively based on a small 7-month effect size of 0.3, a 0.05 type I error, and a 0.01 ICC of students' SSB intake. To achieve 80% power under these assumptions, a total of 12 schools/clusters (6 schools per condition) are needed, with 54 enrolled students per school (and 49 retained after an anticipated 10% attrition rate at student level at 7-month). Following these same assumptions, 99.99% power would be achieved with a total of 12 schools/clusters and an average of ~115 students enrolled per school (and 104 retained after an anticipated 10% attrition rate). In sum, using conservative effect size and ICC estimates and standard type I error rate, enrolling a minimum of 54 students and up to 115 students per 12 schools/clusters would provide adequate power ranging from 80% to 99.9% for the primary 7-month SSB student outcome.

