#### ***Primary effectiveness aim***

Multi-level mixed effect models will be used to control errors of non-independence and heteroscedasticity caused by individual, class and school heterogeneity, and potential covariates identified a priori based on the literature and theory that are relevant to SSB behavior changes. The treatment effect models used in this study will contain outcomes of interest as dependent variables (e.g., SSB kcal, quality of life measures etc.). Specific mixed effect link function will be chosen to fit different outcome distributions. The models will control those unobserved effects that are fixed over time at three different levels (i.e., individual student, class, and school) and

those unobserved time and block fixed effects that are individual-class-school-invariant. To further examine intervention treatment effect differences across blocks, we will modify the models to allow group indicator to interact with time-block fixed effects.

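### The SAP names student health literacy for modelling only as a discrete classification, without classes, cut-offs or link; the item total is probably available and would be a more sensitive main analysis

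*SAP*

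**What the plan says.** The secondary aims in the Protocol's Study Overview list "BMI z-score, theory-related variables, health and media literacy" among the student outcomes, without a metric. The Student Assessment Packet (Protocol, Data Sources) gives the instrument as "Health Literacy & Numeracy, Newest Vital Sign" and states no scoring rule.

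The SAP section on secondary effectiveness, maintenance and reach adapts the primary model by "making the secondary student outcomes the dependent variables". It then adds: "For nonlinear outcomes, such as discrete health literacy classification, appropriate link functions will be used in the multilevel model". This is the only place in either document where the modelled form of student health literacy is named. The general rule, under Primary effectiveness aim, is "Specific mixed effect link function will be chosen to fit different outcome distributions". Neither document states the number of classes, the cut-offs, the link, or whether an item total will be analysed.

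**The concern.** A classification built from an item total treats all students within a class as equal. A student who gains one or two items without crossing a cut-off counts as unchanged. A student who gains one item across a cut-off counts as changed. What the analysis can detect then depends on where students start relative to cut-offs that are not stated.

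The Protocol describes the programme as a behaviour and health literacy curriculum, so change in this outcome is of direct interest. If the finer scale is already in the data, naming only the coarser one gives up sensitivity for no saving. Leaving the cut-offs open also allows them to be chosen after the data are seen.

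**Working it through.** **1. Is a finer scale available?** The Protocol's description of the shortened survey for the continued-support (SupS2) years lets the items be counted.

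- From the main student packet (Attachment 2) to Attachment 37, 36 items were removed. The listed categories sum to 9+3+2+3+11+3+3+1+1 = 36, and none is health literacy.
- The August 2024 change then removed a further 36 items from Attachment 37: 15+6+6+4+5 = 36. These include "health literacy (6 items"), listed separately from public health literacy (4 items).

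Unless items were added without mention, the six health literacy items came from the main packet. One point per item, giving a 0-6 total, is an assumption.

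**2. Steps hidden.** A 0-6 total has six one-point steps. Three classes make 2 visible and hide 4. Two classes make 1 visible and hide 5.

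**3. Student-level information.** The plan gives no power or effect size for this outcome, so there is no figure to reproduce. Under a proportional-odds model, information per student is proportional to 1 - Σp³ over the categories. The relative efficiency of a grouping is (1 - Σp³ grouped) / (1 - Σp³ over seven levels).

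Example with Binomial(6, 0.5), probabilities (1, 6, 15, 20, 15, 6, 1)/64:

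- Seven levels: 1 - 15184/262144 = 0.942.
- Three classes 0-1/2-3/4-6, weights (7, 35, 22)/64: 1 - 53866/262144 = 0.795; ratio 0.843.
- Two classes 0-3/4-6, weights (42, 22)/64: 1 - 84736/262144 = 0.677; ratio 0.718.
- Two classes 0-1/2-6, weights (7, 57)/64: 1 - 185536/262144 = 0.292; ratio 0.310.

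Neither the distribution nor the cut-offs are in the documents, so both were varied: beta-binomial scores on six items, mean proportion correct 0.3 to 0.7, item correlation 0.10 to 0.35, and every possible split.

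| Grouping | Kept, best-placed cuts | Kept, worst-placed cuts (lowest) |
|---|---|---|
| Three classes | 89-94% | about 11% |
| Two classes | 73-79% | about 2% |

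The best-placed loss is therefore 6-11% with three classes and 21-27% with two. The worst-placed figures are extremes in which almost all students fall into one class.

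**4. Effect of clustering.** Information lost within schools matters less when part of the variance lies between schools. The SAP's power section gives "a small 7-month effect size of 0.3, a 0.05 type I error, and a 0.01 ICC of students' SSB intake" and 104 students retained per school. Borrowing that ICC for health literacy is an assumption. If grouping keeps a fraction r of student-level information, the net fraction kept is

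r × (1 + 103 × 0.01) / (1 + (104r - 1) × 0.01) = 2.03r / (0.99 + 1.04r).

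- r = 0.843: 1.711/1.867 = 0.92, so a 16% loss becomes about 8%.
- r = 0.89 to 0.94 (best three-class): 0.94 to 0.97, a net loss of about 3-6%.
- r = 0.73 to 0.79 (best two-class): 0.85 to 0.89, a net loss of about 11-15%.
- r = 0.310 (low two-class cut): 0.629/1.312 = 0.48.

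**The case against.** The strongest reply is that the SAP decides nothing here. The words "discrete health literacy classification" follow such as, in a sentence about link functions, and the general rule on links would cover an item total equally well. This stands in part. A reader might infer that the plan commits to the classification and excludes the score, but the documents do not say so. They support only that the classification is the sole form named.

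Second, the 0-6 score appears nowhere. The count of six comes from a list of items removed from the continued-support survey, and that survey's own content list omits general health literacy. The one-point scoring does remain an assumption. The item arithmetic nevertheless points to the main packet, and the argument needs only that six items give a finer total than a few classes.

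Third, the loss may be small. A well-placed three-class ordinal analysis loses little, and clustering shrinks it further. This stands.

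Two further inferences are tempting. One is that small gains are the expected signal. The documents state no expected health literacy effect, and the feasibility gains reported in the Protocol concern beverage behaviours, media literacy and public health literacy. The other is that a null result could come from grouping alone. With most of the information kept under reasonable cut-offs, that does not follow as a general statement.

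**Conclusion.** The point holds as a modest improvement to a secondary analysis. The plan names a coarser scale, leaves its classes, cut-offs and link open, and is silent on a total that the data very probably contain. Any grouping of that total loses information, and the direction is not in doubt.

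The size is in doubt. The student-level losses of 6-11% and 21-27% rest on the assumed score distributions, one point per item and well-placed cuts, and the reduction through clustering rests on an ICC borrowed from beverage intake. None of these is a figure for this trial. In particular, the two-class losses should not be read as a forecast, because the SAP never says that there will be two classes. The primary beverage analysis is unaffected.

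**What to change.** In the SAP section on secondary effectiveness, maintenance and reach:

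- State that the main health literacy analysis uses the total number of items correct at 7 and 19 months. At 3 months only beverage behaviours are surveyed.
- Name one model, either ordinal (cumulative logit) or binomial (number correct out of the items), with the multilevel structure already planned.
- State how baseline enters, consistently with the longitudinal model under Primary effectiveness aim: either as a repeated measure or as a covariate, not both.
- Report the classification as supportive, with its classes and cut-offs written down.
- Confirm the number of items and the scoring rule.
- Date the change and state whether outcome data had been seen. The Protocol anticipated that data collection would end on 2023-12-30.

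The cost is a few sentences and one additional model specification. No new data are needed, and the classification is still reported.

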**Describe the participants in this group.**

One parent/caregiver per 7th grade student enrolled in Kids SIPsmartER is eligible to participate.

The students' parents/guardians who are >18 years of age or older will be invited to participate in the study. Parents/guardians will be excluded if they are non-English speaking.

We anticipate 3180 parents/caregivers to be enrolled in the NIH funded cohorts of the study (IntS, SupS, ConS) and 742 in the Virginia Foundation for Healthy Youth SupS2 cohorts. Of these participants, we anticipate ~70% (2745) will complete paper consent forms.

Parent/guardian (interview subset)

A convenience sample of parents/guardians who consented to participate in the SMS component in intervention, delayed intervention and support schools will be identified by research staff and asked to participate in the interviews. Only parents/guardians who completed the SMS component will be included because the purpose of the interviews is to understand their experience in and satisfaction with the component.

**Will participants in this group be compensated for taking part in your study?** Yes

**Are any of the participants US citizens or US residents?** Yes

This question applies only to participants who are US citizens or US residents.

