- Intervention, Delayed Intervention, Supported schools: Schools that will have the Kids SIPsmartER as a part of regular classroom activities and the option to participate in the research. On the consent forms, parents/guardians will be able to identify if they want their child's survey data and height and weight to be used for the research and if they want to participate in the research (including completing the surveys and text message program). See Attachment 4. Parent/Guardian Informed Consent Agreement for Kids SIPsmartER Program.
  - o Hybrid version for Intervention, Delayed Intervention, Supported school: Same as original version except for the option of virtual classroom activities and removal of measuring heights and weights. See Attachment 22. Parent/Guardian Informed Consent Agreement for Kids SIPsmartER Program COVID.
  - o Qualtrics Hybrid Version for Intervention, Delayed Intervention, Supported school: Same as COVID version except language at the end of the consent form has been adjust to reflect submitting through Qualtrics (e.g., type in your name, directions for signing). See Attachment 23. Parent/Guardian Informed Consent Agreement for Kids SIPsmartER Program COVID Qualtrics
  - o [ADMENDMENT JULY 2021] Qualtrics Version for Intervention, Delayed Intervention, Supported school: Same as original version (Attachment 4) except language at the end of the consent form has been adjust to reflect submitting through Qualtrics (e.g., type in your name, directions for signing). See Attachment 33. Parent/Guardian Informed Consent Agreement for Kids SIPsmartER Program Qualtrics.
- Control schools: Schools where only data collection activities are available. On the consent forms, parents/guardians will be able to identify if they want their child's survey data and height and weight to be used for the research and if they want to participate in the research (including completing the surveys only). See Attachment 5. Parent/Guardian Informed Consent Agreement for Sugar Drink Survey.
  - o [ADMENDMENT JULY 2021] Qualtrics Version for Intervention, Delayed Intervention, Supported school: Same as original version (Attachment 5) except language at the end of the consent form has been adjust to reflect submitting through Qualtrics (e.g., type in your name, directions for signing). See Attachment 34. Parent/Guardian Informed Consent Agreement for Kids SIPsmartER Program Qualtrics.

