**Describe this Data Source.**

Parents/guardians (Cons, IntS, DIntS, SupS). Survey packets will be sent home from school to those who have signed consent to participate in the research at 3 times (baseline, 7- and 19-months).

The measurement packets are the same regardless of intervention or control schools. With the exception of intervention school participants answering questions about their experience with the Kids SIPsmartER program.

See Attachment #3. Data consists of:

Beverage Behaviors, including SSBs (BEV-Q)  
 SSB Theory of Planned Behavior  
 SSB Media Literacy  
 Health Literacy, 3-items valid for self-administration  
 Public Health Literacy  
 Quality of Life  
 SSB Home Environment  
 SSB Parenting Practices/Rules  
 Satisfaction Questions

MODIFICATION 3/16 DUE to coronavirus and school closure: We are requesting a modification to allow for flexibility in working with each of our enrolled schools to distribute and collect parent surveys. The caregiver survey may be distributed and returned via mail or via an on-line Qualtrics links (using UVA Qualtrics Research Suite) sent to the parents via either text or email. The only change to the survey Attachment #3 will be an addition of a current mailing address so that the gift card can be mailed directly to the parent, instead of going home with the student via school.

The changes the survey instrument have been changed and tracked, see:

View File: KSS\_IRB\_Attachment3\_CaregiverPacket\_v3\_SUBMITTED\_mod5\_add mailing address.docx

Parents/guardians (SupS2). Parents/guardians enrolled during in SupS schools will not complete survey packets.

**Will a recording device (e.g. audio, video, photographic) be used to collect data/materials from participants?** No

**Are the participant's identifying information included as part of the data at any time?** Yes, and participant identifiers will NOT retained

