### Data analysis

Effectiveness analysis will be on the individual level. Due to the high degree of homogeneity (in income and race) among the eligible schools, focus will be placed on detecting potential selection bias on the individual level program participation and attrition. Appropriate descriptive, parametric, and non-parametric statistical methods will be used to compare continuous and categorical variables among the intervention conditions at baseline. Data will be examined for the presence of outliers, violations of normality for continuous variables, and missing data. Major violations of normality will be corrected with an appropriate transformation procedure. All analysis will use cluster-robust standard error adjustment.

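### The SMS-uptake term in the secondary caregiver model is a self-selected contrast within programme schools, so it supports an association and not a claim of SMS influence

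*SAP*

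**What the plan says.** In the SAP section on secondary effectiveness, maintenance and reach outcomes, caregiver outcomes are analysed with a simplified form of the primary multilevel model. A further step follows: "an additional indicator that signals the uptake of the SMS will be added to the model to examine the adoption of SMS influence on" caregiver behaviour and the home environment. The next sentence says that "mixed effect structural equation models will examine the causal relationship among caregiver and student SSB outcome changes".

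Three statements elsewhere in the SAP bear on selection:

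- Under Primary effectiveness aim, the models include "potential covariates identified a priori based on the literature and theory that are relevant to SSB behavior changes". No covariate is listed.
- The same section says: "The models will control those unobserved effects that are fixed over time at three different levels".
- Under Data analysis, "focus will be placed on detecting potential selection bias on the individual level program participation and attrition".

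The caregiver sentence also calls the models selection models, but the primary section to which it refers back describes no selection equation.

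In the protocol, schools are randomised to the whole programme or to control. Control caregivers complete evaluations only (Study Logistics). Texting is delivered together with the student curriculum, and caregivers are told that taking part is voluntary (Risks & Benefits). Uptake is not defined. The programme consent form asks caregivers "if they want to participate in the research (including completing the surveys and text message program"). For the interview subset, the protocol separates caregivers who consented to texting from those who completed it: "Only parents/guardians who completed the SMS component will be included".

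**The concern.** The words *influence* and *causal relationship* are attached to exposures that nobody randomised. A caregiver who signs up for, answers or finishes a texting programme is plausibly one who was more ready to change household drinking habits anyway. If so, a favourable uptake coefficient could appear although the texts did nothing, and it could be reported as evidence that texting works. Texting is the component that is meant to engage caregivers, and caregiver behaviour and the home environment are stated secondary outcomes, so such a statement would be used.

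The group coefficient printed beside the uptake coefficient carries a second risk. It could be read as the programme effect on caregivers when it is no longer the randomised comparison. The structural model has the same difficulty as the uptake term: caregiver change and student change are both outcomes, and neither is randomised with respect to the other.

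**Working it through.** The SAP gives no uptake rate, caregiver effect size or power for this analysis, so there is no figure to reproduce. The identification argument needs no assumed number; the size does.

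**1. What the model estimates.** Write caregiver change as b0 + b1·G + b2·U, with G = programme school and U = uptake.

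| Cell | Mean |
|---|---|
| Control (U always 0) | b0 |
| Programme, no uptake | b0 + b1 |
| Programme, uptake | b0 + b1 + b2 |

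There is no control cell with uptake. Hence b2 is uptakers minus non-uptakers within programme schools, and b1 is programme non-uptakers minus all controls. The randomised contrast is b1 + p·b2, where p is the uptake share. The model without U estimates it directly.

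**2. The safeguards.**

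- Effects fixed over time remove stable differences in level. They leave differences in how much a caregiver was going to change, which is the confounder here.
- A priori covariates help as far as they measure readiness to change. They are not named.
- Selection models are named without an equation, an instrument or an exclusion restriction.
- The attention to selection bias concerns detection, for participation and attrition. No correction for SMS uptake is stated.

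**3. Size, by illustration.** Every input is assumed: p = 0.4 to 0.8; r1 = correlation of latent uptake with motivation, 0.3 to 0.5; r2 = correlation of motivation with change, 0.2 to 0.3; q = correlation of a baseline theory measure with motivation. The protocol's 76–82% of adults using SMS describes use in the region and is not an uptake rate. The true SMS and programme effects are zero. Let f be the normal density at z(1−p). Positive means favourable change.

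Spurious uptake coefficient = r1·r2·f·(1−q²) / [p(1−p) − 0.5·(q·r1·f)²]; shift in the group coefficient = −p times that.

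Upper end, q = 0: p = 0.8 gives f = 0.280, so 0.5 × 0.3 × 0.280 / 0.16 = 0.26, and the shift is −0.8 × 0.26 = −0.21. Lower end of the grid: p = 0.5 gives f = 0.399, so 0.3 × 0.2 × 0.399 / 0.25 = 0.096.

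| q | Uptake coefficient (SD of change) | Group shift (SD) |
|---|---|---|
| 0 (unadjusted) | 0.10 to 0.26 | −0.04 to −0.21 |
| 0.5 | 0.07 to 0.20 | −0.03 to −0.16 |
| 0.7 | 0.05 to 0.14 | −0.02 to −0.11 |
| 0.9 | 0.02 to 0.05 | −0.01 to −0.04 |

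With r1 = 0 the bias is zero. With r1 = r2 = 0.1 and p = 0.6 it is 0.01 × 0.386 / 0.24 = 0.016 SD.

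**4. Checks by simulation.** With 400,000 caregivers, p = 0.8, r1 = 0.5, r2 = 0.3 and q = 0.5, the uptake coefficient was 0.266 unadjusted and 0.203 adjusted. The group coefficient was −0.211 and −0.160, and 0.002 once the uptake term was removed.

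A second simulation used 6 + 6 schools, 3180/30 = 106 caregivers per school, the student ICC of 0.01, and a direct correlation between readiness to take up and change. A correlation of 0.1 gave 0.16 to 0.17 SD in favour of uptakers at 50–82% uptake. A correlation of 0.2, above the products r1·r2 of 0.06 to 0.15 used in step 3, gave 0.33 to 0.35 SD. The intervention-minus-control mean stayed within 0.006 SD of zero throughout.

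**The case against.** The strongest reply is that the SAP claims less than this point rebuts. A reader might infer that the plan presents the uptake coefficient as a randomised SMS effect. It does not: the indicator is an addition to a secondary analysis, and the protocol speaks of exploring caregiver outcomes. A reader might also infer that the caregiver programme effect is lost. The order of the text points the other way, with the caregiver model first and the indicator added afterwards. Both parts of the reply stand. What remains is causal wording with no stated caveat or identifying assumption.

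Uptake might also mean consent. The programme consent form covers surveys and texting together, and on that coding the indicator would largely duplicate arm. The consented/completed distinction comes from an interview eligibility rule, and the SAP's closest gloss is a line under reach saying that SMS uptake and utilisation will be analysed. A measure that varies within programme schools is the natural reading, but the SAP should say so.

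The magnitudes are assumed throughout, as shown, and other choices move them a long way in either direction. It is tempting to turn them into a rate of false findings. The documents do not support one. It would rest on the same guesses, and the SAP requires cluster-robust errors, which with 12 schools rejected in 8.6 to 9.9% of simulated runs with no selection at all.

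Finally, restricting the analysis to programme schools removes no bias by itself: without covariates the coefficient is the same contrast. That is correct, and the fix does not rely on it.

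**Conclusion.** The concern holds, as a minor point. The uptake coefficient is a self-selected contrast within programme schools, and the group coefficient beside it is not the randomised programme effect. This follows from the design, given that uptake varies within programme schools and arm stays in the model. The stated safeguards may shrink the self-selection but cannot be relied on to remove it.

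The size is not derivable from the documents. Under the assumed ranges it lies between about 0 and about 0.26 SD unadjusted, and less with a good baseline measure of motivation. The bias is nil if uptake is unrelated to readiness to change, but the SAP offers no way to show that. The randomised caregiver contrast from the model without the uptake term, and the primary student analysis, are untouched.

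**What to change.** In the SAP section on secondary effectiveness, maintenance and reach outcomes:

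1. State that the caregiver programme effect is taken only from the as-randomised model without the uptake term.
2. Define uptake as participation or engagement recorded by the text system, and analyse it within programme schools. Adjust for the baseline outcome and for named theory-based measures already in the caregiver packet, such as "SSB Theory of Planned Behavior", media literacy, health literacy and home environment. Report the result as an association. Note that the adjustment, and not the restriction to programme schools, is what reduces the bias. Note also that some texts ask about drinking behaviour and home availability, so replying may itself depend on change.
3. Describe the caregiver-student structural model as estimating an association instead of a causal relationship.

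No new data are needed, since the text data and baseline measures are already collected. The cost is that these secondary results support weaker claims. If engagement is counted from replies, caregivers who read without replying will be classed as less engaged.
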